5.6 Compliance Criteria

Treatment breaks must be clearly indicated in the treatment record along with the reason(s) for the treatment break(s). Treatment breaks, if necessary, should ideally not exceed five treatment days at a time and ten treatment days total. Treatment breaks should be allowed only for resolution of severe acute toxicity and/or for intercurrent illness and not for social or logistical reasons. Treatment or visit delays for public holidays or weather conditions do not constitute a protocol violation.

Institutions are encouraged to generate treatment that fall within the dose limits defining the per protocol category. For those target to critical structures geometries that are more challenging, some variation from the specified protocol dose limits is acceptable.

6 Study Procedures and Observations

6.1 Schedule of Procedures and Observations

The study-specific assessments are detailed in this section and outlined in [Section 6 Schedule of Study Procedures and Assessments](#). Screening assessments must be performed within 28 days prior to the first dose of investigational product unless otherwise noted. Any results falling outside of the reference ranges may be repeated at the discretion of the investigator. All on-study visit procedures are allowed a **window of ± 3 days** unless otherwise noted. Treatment or visit delays for public holidays or weather conditions do not constitute a protocol violation.

A written, signed, informed consent form (ICF) and a Health Insurance Portability and Accountability Act (HIPAA) authorization must be obtained before any study-specific assessments are initiated. A copy of the signed ICF will be given to the subject and a copy will be filed in the medical record. The original will be kept on file with the study records.

All patients who are consented will be registered in OnCore[®], the UCSF Helen Diller Family Comprehensive Cancer Center Clinical Trial Management System (CTMS). The system is password protected and meets HIPAA requirements.

6.1.1 Pretreatment Period

6.1.1.1 Screening Assessments

The Screening procedures and assessments must be completed within 14 days of the Day 1 Visit unless otherwise noted.

- Physical examination - The initial complete physical examination should include evaluation of the head, eyes, ears, nose and throat (HEENT); cardiovascular, dermatological, musculoskeletal, respiratory, gastrointestinal, and neurological systems. Height and weight will also be recorded.
- Vital signs
- Complete medical history – can be done within 28 days of Day 1
- Baseline conditions assessment
- Documentation of disease assessment - Assessments should include an evaluation of all sites of disease. Patients will undergo tumor assessments per RECIST version 1.1 tumor response criteria. Can be done within 28 days of Day 1
- Performance status
- Skindex-16 questionnaire
- History of prior treatments and any residual toxicity relating to prior treatment
- Baseline medications taken within 28 days of Day 1

- Laboratory assessments
 - Hematology (hemoglobin, hematocrit, platelet count, RBC count, WBC count, percent and absolute differential count [neutrophils, bands, eosinophils, lymphocytes, monocytes, basophils, other cells])
 - Serum chemistries (sodium, potassium, chloride, bicarbonate, glucose, BUN, creatinine, calcium, alkaline phosphatase, magnesium, total bilirubin, albumin, total protein, ALT, AST, and as clinically indicated; LDH, and phosphorus)
 - Pregnancy test: All women of childbearing potential (including those who have had a tubal ligation) will have a serum pregnancy test at screening, within 7 days of Day 1.
 - Urine or serum pregnancy tests will be performed every 4 weeks at specified subsequent visits. If a urine pregnancy test is positive, it must be confirmed by a serum pregnancy test.
 - Urinalysis
- Imaging (CT or MRI) of primary tumor region and any involved regional lymph nodes for tumor assessment. Can be done within 28 days of Day 1
 - Note: The CT scan with contrast or an MRI with gadolinium must be done unless medically contraindicated. The MRI or CT scan must encompass the skull base and/or upper mediastinum if those areas are involved. If locally advanced BCC lesions with a RECIST-measurable component are identified, the same imaging modality used at baseline must be used throughout the study.
- Chest x-ray or chest CT scan, or CT of chest and abdomen – can be done within 28 days of Day 1
- For externally visible tumors
 - Bidimensional measurements of externally visible tumor dimension
 - Description of the lesion at baseline
 - Digital photography of target lesion(s)
 - Tumor biopsy for pathologic diagnosis - can be done within 360 days prior to Day 1

The following pre-treatment evaluations/interventions are not required but are highly recommended:

- PET/CT scan for patients with suspected metastatic disease
- Brain MRI for patients with disease located at or near the skull base
- Biopsy confirmation of suspected involved regional nodes (fine needle aspiration is acceptable);
- For patients with head and neck cancers who will have treatment-related risk to salivary function, pre-radiotherapy dental evaluation is strongly recommended

6.1.2 Treatment Period

6.1.2.1 Study Procedures, Week 5 and 9 (Induction Phase)

- Physical examination including weight
- Vital signs
- Performance status
- Evaluation of adverse events
- Concomitant medications

- Skindex-16 survey
- Laboratory assessments
 - Hematology
 - Serum chemistries
- Urine or serum pregnancy tests at weeks 5 and 9 - if a woman of childbearing age

6.1.2.2 Study Procedures, Week 13-14 (End of Induction)

Within 14 days after completion of induction vismodegib therapy, patients must have a re-evaluation to determine if there has been disease progression prior to starting concurrent treatment. Patients whose disease has progressed will no longer continue on study.

- Physical examination including weight
- Vital signs
- Performance status
- Evaluation of adverse events
- Concomitant medications
- Skindex-16 survey
- Laboratory assessments
 - Hematology
 - Serum chemistries
- Urine or serum pregnancy tests - if a woman of childbearing age
- Disease assessment
- Imaging (CT or MRI) of head and neck for tumor assessment
- CT chest or chest x-ray – if clinically indicated
- For externally visible tumors
 - Bidimensional measurements of externally visible tumor dimension
 - Standardized digital photography of target lesion(s)

6.1.2.3 Study Procedures, Week 15-21 (Radiation Therapy)

Three-dimensional conformal therapy is required for this study. IMRT is allowed as deemed appropriate and is highly encouraged for very advanced disease presentations.

Following conclusion of induction drug therapy and completion of re-evaluation procedures, radiation should start within 1 to 14 days after completion of induction vismodegib, unless there is an unforeseen delay. During the re-evaluation interval, vismodegib will continue to be given daily until radiation therapy starts. Radiation therapy is anticipated to last approximately 7 weeks depending on the prescription dose chosen by the study investigator.

Note: If there is an unforeseen delay in starting the radiation therapy, an additional 1-2 weeks of treatment with vismodegib may be given after contacting and getting the consent of the Principal Investigator. If there is a delay over 4 weeks in initiation of radiation therapy, investigators should consider removal of the patient from the protocol.

While receiving radiation therapy, patients will have limited physical exams, evaluation of adverse events, and assessment of concomitant medications weekly. At week 18 only, patients will have urinalysis, pregnancy test, and laboratory assessments (hematology and serum chemistries). The drug diary will be collected at week 18.

Radiation therapy will be 66-70 Gy in 33-35 fractions over 7 weeks as prescribed in Section 5.2. See section 5 for Radiation Therapy treatment planning, imaging, and localization requirements.

6.1.3 End-of-Treatment Study Procedures

To be completed within 8 – 12 weeks of the last dose of study drug.

- Physical examination including weight
- Vital signs
- Performance status
- Evaluation of adverse events
- Concomitant medications
- Skindex-16 survey
- Laboratory assessments
 - Hematology
 - Serum chemistries
- Urine or serum pregnancy tests within 4 weeks after completion of radiation therapy - if a woman of childbearing age
- Disease assessment
- Imaging (CT or MRI) of head and neck for tumor assessment
- CT chest or chest x-ray – if clinically indicated
- For externally visible tumors
 - Bidimensional measurements of externally visible tumor dimension
 - Digital photography of target lesion(s)
 - Description of the lesion
 - Tumor biopsy – as needed to confirm progression

If biopsy results are confirmatory of persistent cancer, the patient may be offered salvage surgery as indicated. This would result in discontinuation from the study. Post-salvage follow-up may be conducted by UCSF investigators with separate consent by the patient.

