2.2 Secondary

- To estimate of the probability of progression free survival (PFS), with failure defined as any disease recurrence or death due to any cause, and overall survival (OS) with the duration for each measured from the time of first treatment with vismodegib to 12 months after completion of study treatment.
- To evaluate toxicity during the drug-alone and combined-modality components of the protocol regimen during treatment. This will be assessed by

- The number and attribution of all adverse events, (including vital signs, physical findings, and clinical laboratory results, CTCAE, v 4.0) in patients who receive any amount of study drug and radiation therapy.
- The proportion of any adverse events (CTCAE, v. 4.0) assessed to be definitely, probably, or possibly related to vismodegib or its combination with radiation therapy.
- The proportion of patients experiencing Grade 4-5 adverse events assessed to be definitely, probably, or possibly related to the induction or concurrent treatment components of the protocol regimen (that is not definitely related to disease progression).
- To evaluate initial toxicity during the 3 months immediately after completion of protocol therapy.
- To estimate the feasibility of administering concurrent vismodegib with radiation therapy determined by the proportion of patients discontinuing treatment due to toxicity during the concurrent administration of vismodegib and radiation therapy (<75% of planned radiation therapy delivered)
- To evaluate the response rate (as per RECIST) at completion of protocol therapy of the primary site and regionally involved areas in subjects with measurable disease prior to initiation of therapy at 3 months after the completion of protocol therapy.
- To evaluate the clinical response to vismodegib and radiation therapy determined by the proportion of patients with a decrease of BCC within the irradiated planning tumor volumes (PTVs) in patients who complete the combined therapy.

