The duration of overall CR is measured from the time measurement criteria are first met for CR until the first date that recurrent disease is objectively documented.

Duration of stable disease

Stable disease is measured from the start of the treatment until the criteria for progression are met, taking as reference the smallest measurements recorded since the treatment started.

Progression-Free Survival

Progression-free survival (PFS) is defined as the duration of time from start of treatment to time of progression or death due to any cause.

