7.3 Assessment of Failure Patterns

Local or Regional Relapse

Relapse is defined as reappearance of tumor after complete response. If possible, relapse should be confirmed by biopsy.

Local or Regional Progression

Progression is defined as an estimated increase in the size of the tumor (product of the perpendicular diameters of the two largest dimensions) of greater than 20%, taking as reference the smallest value of all previous measurements or appearance of new areas of malignant disease. This should be compared to radiology reassessment done after the completion of radiation therapy.

Distant Metastasis Progression

Progression of a distant metastasis (e.g. lung, bone, brain, liver) is defined as an estimated increase in the size of the tumor (product of the perpendicular diameters of the two largest dimensions) of greater than 20%, taking as reference the smallest value of all previous measurements or appearance of new areas of malignant disease. This should be compared to radiology reassessment done after the completion of radiation therapy.

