The secondary clinical aims of the duration of progression free survival (PFS) and overall survival (OS) will be measured from the start of protocol therapy until death due to any cause or until the first evidence of any disease progression, or death, respectively. Point estimates (e.g. median, percent PFS at 12 months) with 95% confidence intervals will be calculated using the Kaplan-Meier product limit method to summarize results. Based upon RECIST criteria, the proportion of patients responding in the primary site and regionally involved areas at 3 months after completing protocol therapy will be determined and presented with 95% confidence intervals. The proportion of patients achieving any decrease in BCC within the boundaries of the treated radiation PTV area will be determined and presented with a 95% confidence interval. In addition, the proportion of patients who start concurrent vismodegib and radiation therapy and receive at least 75% of the planned radiation therapy will be determined and presented with a 95% confidence interval to summarize the feasibility of administering concomitant therapy.

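### Salvage surgery for biopsy-proven persistent cancer without progression ends study participation but is not a PFS event, and section 8.5 has no rule for such patients

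*Combined protocol and SAP*

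**What the plan says.** - **Exit from study.** Section 6.1.3 (End of Treatment, weeks 29-33 in Table 6.1) states that if biopsy confirms persistent cancer, "the patient may be offered salvage surgery as indicated. This would result in discontinuation from the study". Later observation is optional: "Post-salvage follow-up may be conducted by UCSF investigators with separate consent by the patient". Section 6.1.5 takes a patient off protocol for any non-protocol treatment of the treated local or nodal site, and allows long-term follow-up to stop once new treatment begins.
- **PFS event.** Section 2.2 has "failure defined as any disease recurrence or death due to any cause". Section 7.2 has PFS "defined as the duration of time from start of treatment to time of progression or death due to any cause". Sections 8.2 and 8.5 name recurrence or progression, and death.
- **What counts as progression or relapse.** Section 7.2.1.4 requires a rise of at least 20% and 5 mm over the nadir, or a new lesion in the irradiated PTV. Section 7.3 also requires growth or new disease for local progression, and says "Relapse is defined as reappearance of tumor after complete response".
- **Estimator.** Section 8.5 says that PFS point estimates with 95% intervals "will be calculated using the Kaplan-Meier product limit method to summarize results". It gives no censoring rule and no rule for new anticancer treatment.
- **Conservative failure rule.** Sections 8.5 and 8.5.1 count some removed patients as failures. The rule covers local-regional control only, and only patients removed before 75% of radiotherapy without a documented response.

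**The concern.** A patient who completes radiotherapy, has a partial response or stable disease, and has a biopsy positive for residual cancer meets none of the PFS event wordings. If salvage surgery follows, participation ends, and the operation removes the lesion in which progression would have been measured. Kaplan-Meier treats a patient whose follow-up stops without an event as having the same later risk as those still observed. Here the reason for leaving is proof that cancer survived the regimen, so that assumption is doubtful.

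PFS is the first-listed secondary endpoint. If a few patients take this route, the reported curve could look better than the regimen deserves, and its confidence interval would not show it. Without a rule set in advance, the coding would also be chosen after the results are known.

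**Working it through.** **1. The plan's own figure.** The plan assumes no PFS rate. Its one quantitative design claim is 81% power for local-regional control (section 8.3.1). Exact binomial with n = 24:
- P(X ≥ 18 | 0.60) = 0.096, and P(X ≥ 17 | 0.60) = 0.192, so the cut-off at one-sided 0.10 is 18.
- P(X ≥ 18 | 0.80) = 0.811.

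The 81% reproduces, and it does not depend on how PFS is coded.

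**2. Who is affected.** Patients with a positive biopsy at End of Treatment:

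| Status at the visit | PFS event already? |
|---|---|
| Meets progressive disease (7.2.1.4) | Yes |
| Reappearance after complete response (7.3) | Yes |
| Partial response or stable disease, residual cancer on biopsy | No |

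Only the third row, followed by salvage surgery or other local treatment, is at issue.

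**3. Timing.** Weeks 29-33 are 29 × 7/30.4375 = 6.7 to 33 × 7/30.4375 = 7.6 months from the start. Section 8.2 reports PFS 12 months after therapy: 21 × 7/30.4375 + 12 = 16.8 months. Section 8.5 also mentions PFS at 12 months. The exit precedes both.

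**4. Difference between the two codings.** Inputs: n = 24 from section 8.3.1. As assumptions, k patients salvaged at End of Treatment, three other PFS events after that visit and before the landmark, and no other loss.
- Censored: S = (24 − k − 3)/(24 − k)
- Counted as failures: S = (24 − k − 3)/24, with SE = √(S(1 − S)/24)

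| k | Censored | Failure | Gap (points) | Gap / SE |
|---|---|---|---|---|
| 1 | 20/23 = 87.0% | 20/24 = 83.3% | 3.6 | 0.48 |
| 2 | 19/22 = 86.4% | 19/24 = 79.2% | 7.2 | 0.87 |
| 3 | 18/21 = 85.7% | 18/24 = 75.0% | 10.7 | 1.2 |
| 4 | 17/20 = 85.0% | 17/24 = 70.8% | 14.2 | 1.5 |

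Other event patterns give similar gaps. One event before the visit and two after: 3.8 points for k = 1 and 14.9 for k = 4. Two before and four after: 3.4 and 13.0.

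**5. Why these are upper limits.** Take k = 2, and let j of the two be patients who would have progressed or died by the landmark without surgery. PFS would then have been (24 − 3 − j)/24, against a censored estimate of 86.4%:
- j = 0: 87.5%, error −1.1 points
- j = 1: 83.3%, error +3.0 points
- j = 2: 79.2%, error +7.2 points

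The full gap is reached only if every salvaged patient would have failed. Censoring implicitly gives these patients the risk of those who remain, 3/22 = 13.6%. The estimate is too high if their true risk exceeds that, which is likely with proven residual cancer but is not shown by the documents.

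**The case against.** **Censoring is not written anywhere.** True. Section 8.5 names the estimator and stops. Censoring is what Kaplan-Meier does by default when follow-up ends without a defined event, so the fault is a missing rule rather than a wrong rule chosen.

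**The biopsy is for progression.** Section 6.1.3 lists "Tumor biopsy – as needed to confirm progression", so many positive biopsies may come from patients who are already PFS events. This narrows the group but does not empty it, because the trigger for salvage is persistent cancer, not progression.

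**Salvage may be rare.** Entry under section 3.3.1 requires disease considered inoperable or a contraindication to surgery, which limits who can later be operated on. That section also admits patients who refused surgery or for whom it would be disfiguring, and the protocol provides for salvage. A reader might infer two to four cases from the 20% to 40% failure implied by the design hypotheses. The documents do not support this: those rates cover every patient without control at 12 months, including ordinary progression.

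**Follow-up may continue.** Section 3.5 promises 12 months or until death, and section 6.1.5 only permits follow-up to stop, so some deaths may be captured. This offsets the problem in part, since progression in the removed lesion cannot be observed.

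**Counting salvage as failure alters the endpoint.** It is broader than progression or death, and two patients with the same biopsy are coded differently if only one has surgery. This stands, and is the reason to report both codings.

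**PFS is descriptive.** Section 8.5 attaches no test to it. This limits the consequence but does not make the estimate interpretable.

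**Conclusion.** The gap is real and specific. The PFS event definition and the discontinuation rule together let a patient with biopsy-proven residual cancer, but no progression or relapse, leave before the landmark without an event, and no rule in the plan covers this. The same can happen under section 6.1.5 when other non-protocol treatment of the irradiated site takes a patient off protocol and follow-up ceases.

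The default handling is probably informative and would tend to raise PFS, by at most about 3 to 4 points per patient with 24 patients and the event counts assumed here. A reader might conclude that PFS is certainly inflated, or that every salvaged patient raises it by the full amount. The documents do not support that: censoring is inferred, the number salvaged is unknown, and some salvaged patients might not have progressed by the landmark. The primary test and its power are not affected. The change should be made, but the trial does not fail without it.

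**What to change.** In section 8.5, and in the PFS definitions in sections 7.2 and 8.2:
- State that biopsy-confirmed persistent BCC followed by salvage surgery, or by other non-protocol treatment of the irradiated site, counts as a PFS failure. State the event date. The biopsy date is the practical candidate, since biopsy is a listed study procedure; the documents do not show that surgery dates are collected.
- Report PFS with these patients censored as a sensitivity analysis, and give their number.
- Reconcile section 3.5 (follow-up for 12 months or until death) with sections 6.1.3 and 6.1.5.

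The cost is a short definition and one extra estimate. The failure-counted PFS will be less favorable, and it is a slightly broader endpoint than progression or death, which the report should say. Sample size and the primary analysis stay as they are.

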6.1.4 Post-treatment/Follow Up Visits

Patients will be followed at 3, 6, and 12 months (+/- 2 weeks) after the End of Treatment visit or until disease progression. The following procedures will be performed at the Follow-Up Visit(s):

- Evaluation of clinical response or deterioration
- Physical examination including weight
- Vital signs
- Performance Status
- Evaluation of adverse events
- Concomitant medications
- Skindex-16 survey
- Laboratory assessments
 - Hematology

- Serum chemistries
- Urine or serum pregnancy tests - if a woman of childbearing age – at 3 and 6 month visits only
- Disease assessment
- Imaging (CT or MRI) of head and neck for tumor assessment
- CT chest or chest x-ray – if clinically indicated
- For externally visible tumors
 - Bidimensional measurements of externally visible tumor dimension
 - Digital photography of target lesion(s)
 - Description of the lesion
 - Tumor biopsy - to confirm progression

